#### Categorical variables

For variables with 2 categories, Chi-square test will be used to evaluate the association between variables if the expected values in each cell are  $\geq 5$  in at least 25% of the cells. When the expected values are  $< 5$  in more than 25 % of the cells, Fisher's exact test will be used.

To assess the association between two polytomous variables ( $>2$  categories), the Pearson's Chi-square test will be used if the frequency expected is  $\geq 5$  in at least 75% of the cells. If not, we will regroup to increase the expected frequencies.

#### Continuous variables

Normality of continuous variables will be assessed using the Shapiro-Wilk test. For non-normal variables showing a significant positive skewness, logarithmic, square-root, exponential, or inverse transformation will be applied. For those variables which will not show a normal distribution after arithmetic transformation, non-parametric tests will be used.

### *Continuous variables without repeated measures*

For those variables which will show a normal distribution at the Shapiro-Wilk test, an independent two-sample T test will be performed to check differences between groups, whereas ANCOVA analysis will be performed to include covariates in the analysis.

Differences between groups of non-normally distributed variables will be assessed by Mann-Whitney U test, while non-parametric analysis of covariance (Quade's test) will be used to explore the effects of any covariates.

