## Allocation

Subjects who will be assessed as eligible and will accept to enter the study protocol, will be allocated in the proper group, and the enrollment will be concluded when 2 groups of subjects will be constituted as follows:

- **Group 1**, habitual milk consumers (HMC): 20 subjects who are regular milk consumers ( $>700$  mL/week), do not experience GI discomforts after milk intake and are lactose tolerant or lactose malabsorber.
- **Group 2**, non-habitual milk consumers (NHMC): 20 subjects who are not regular milk consumers ( $< 150$  mL/week), because of GI discomforts after milk intake and are lactose tolerant or lactose malabsorber.

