### *Continuous variables with repeated measures*

Normality of measures, for each time, will be assessed using the Shapiro-Wilk test.

Differences of variables between baseline and over time within and between the groups, for normally distributed variables, will be tested by ANOVA with repeated measures on one factor (time) and Bonferroni adjustment for multiple comparisons. For non-normally distributed variables, Friedman test and pairwise Wilcoxon as a *post hoc* test will be applied.

Analysis of quartiles will be performed for both baseline values and pairwise time points ( $\Delta$ ) upon milk ingestion.

For these variables with repeated measures, the total area under the curves (AUCs) will be also estimated using the linear trapezoidal rule, and differences in AUCs between the groups will be assessed by proper parametric or non-parametric analyses including as covariates the potential confounding variables measured at baseline.

Pearson's correlation coefficients will be calculated to assess bivariate associations among continuous variables at baseline or partial associations of estimated AUCs controlling for baseline values for variables with repeated measures.

Spearman's rank correlation will be used to assess association between non-parametric variables collected and microbiota related variables (e. g. species abundance and genes abundance).

In order to explore differences in microbiome profiles, a Partial Least Squares Discriminant Analysis was applied.

Furthermore, principal component analyses (PCA) on specific variables at baseline or unstandardised residuals correlation between AUCs and related baseline values will be also performed in order to extract features relevant to the cluster structure. Moreover, statistical significance of the distance between groups in the PCA analysis will be computed using the Hotelling T2 test.

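### Quade's test, the plan's only named non-parametric covariate adjustment, shrinks the group difference when the covariate differs between these non-randomised groups; a model containing group avoids this

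*Combined protocol and SAP*

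**What the plan says.** All references are to the combined protocol and SAP.

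- **Continuous variables.** Normality is checked by Shapiro-Wilk. Positively skewed variables are transformed first, and only those still non-normal go to non-parametric tests.
- **Continuous variables without repeated measures.** Normal variables get a t test, or ANCOVA when covariates are included. For the rest, "Differences between groups of non-normally distributed variables will be assessed by Mann-Whitney U test". The adjusted method is "non-parametric analysis of covariance (Quade", that is, Quade's test, and its stated role is to explore covariates.
- **Continuous variables with repeated measures.** Non-normal repeated measures go to Friedman and pairwise Wilcoxon tests. AUCs are compared between groups by "proper parametric or non-parametric analyses including as covariates the potential confounding variables measured at baseline". Quade's test is not named here, but no other non-parametric method that takes a covariate appears anywhere in the plan.
- **Allocation.** Eligible subjects "will be allocated in the proper group": one group is "20 subjects who are regular milk consumers" (above 700 mL/week) without discomfort, and the other drinks under 150 mL/week "because of GI discomforts after milk intake and are lactose tolerant or lactose malabsorber". There is no randomisation.

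The plan names no covariates. It does not mention the equal-distribution assumption, and it gives no check or fallback if that assumption fails.

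**The concern.** Quade's test ranks the outcome and the covariate, regresses one on the other over all subjects with group left out, and compares the residuals between groups. If the covariate differs between groups, the pooled slope picks up part of the group effect, and the residual comparison loses it. Randomisation would make equal covariate distributions plausible. Groups chosen by milk intake and symptoms do not, and a variable confounds only if it is associated with group.

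The parametric branch does not share the fault, because ANCOVA holds group and covariate in one model. A Shapiro-Wilk result would therefore decide whether an adjusted difference is attenuated, which has nothing to do with the scientific question. What is at stake is a missed or understated adjusted difference, mainly in AUCs of the postprandial endpoints that remain non-normal. The same would apply to the optional comparison of lactose-tolerant and malabsorber subgroups under Further analyses, which are not randomised either.

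**Working it through.** **Inputs from the plan.** 20 per group (Sample size calculation, Allocation); two-sided 0.05 (Statistical analysis); 19 per group said to give 80% power for a 40% difference in BCM-7.

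**The plan's own figure.** The 19 cannot be reproduced, because the SD behind it is only cited. It is not disputed here and serves only to set a plausible effect size. Solving n = 2(1.96 + 0.84)²/d² for n = 19 gives d = 0.909, a coefficient of variation of 0.40/0.909 = 44%. The t-test version gives d = 0.934 (43%). An effect of 0.93 is used below.

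**Algebra.** Let e be the residual of outcome rank on covariate rank, pooled over groups. By the partial-regression identity, with b the group coefficient from a rank model containing both group and covariate:

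mean(e, group 2) − mean(e, group 1) = (1 − R²) × b

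R² is the squared correlation of group with covariate rank. The factor never exceeds 1, so the shrinkage is always toward zero, whichever way the covariate acts. The identity held to three decimals in every simulated data set.

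**Simulation.** 20,000 trials per setting, 20 per group, skewed outcome. Assumed, not from the documents: within-group covariate-outcome correlation 0.5; a group effect of 0.93 of the SD left after the covariate (0.93 × √(1 − 0.5²) = 0.81 of the within-group SD); a covariate mean shift of 0 to 2 SD in the same direction as the effect. The comparator is rank ANCOVA with group in the model.

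| Covariate shift | Mean 1 − R² | Power, Quade | Power, group in model | Type I error, Quade |
|---|---|---|---|---|
| 0 SD | 0.97 | 77.7% | 77.9% | 4.8% |
| 0.5 SD | 0.92 | 75.3% | 77.5% | 4.5% |
| 1 SD | 0.78 | 63.4% | 72.9% | 3.3% |
| 1.5 SD | 0.61 | 43.3% | 64.7% | 1.9% |
| 2 SD | 0.46 | 22.6% | 55.4% | 0.7% |

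Type I error of the comparator ran from 4.8% to 6.3%. With the covariate acting in the opposite direction, power was 55.4% vs 66.6% at 1 SD and 15.5% vs 48.5% at 2 SD. At correlation 0.7 the loss was again about 3 points or less at 0.5 SD (74.4% vs 76.8%, or 68.0% vs 71.0%, by direction), and the comparator's type I error reached 7.7% at 2 SD. A separate run of 6,000 trials per setting, with an effect of 0.9, gave the same shrinkage factors.

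**Same comparison at equal error rates.** With both tests calibrated to 5%, power is 0.70 vs 0.72 at 1 SD, 0.58 vs 0.60 at 1.5 SD and 0.50 vs 0.52 at 2 SD. Most of the gap at nominal 5% is therefore Quade's conservatism, plus some liberality in the comparator.

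**Ordinal alternative.** A small check of cumulative-logit regression (20 per group, 400 trials per setting) gave type I error of 5.0%, 5.8% and 6.8%, and power of 80%, 72% and 52%, at shifts of 0, 1 and 2 SD. With 400 trials, the standard error of the 6.8% is √(0.068 × 0.932/400) = 1.3 points.

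**The case against.** The strongest reply concerns reach. Skewed variables are transformed first, so a lognormal outcome would normally end in the t test or ANCOVA. Peptide and hormone profiles that stay non-normal go to Friedman and Wilcoxon tests. Quade's test is named only for variables without repeated measures, and there its stated role is to explore covariates, with Mann-Whitney as the group comparison. Its use for AUCs is an inference. All of this stands and limits the point. It does not remove it, because the plan offers no other non-parametric way to meet its own requirement of covariate-adjusted AUC comparisons.

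Three stronger readings are tempting, and the documents do not support them.

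- **That the assumption is known to fail here.** Only milk intake and symptoms differ by definition. Both groups share the BMI limits and exclusions, no covariate is named, the plan speaks of potential confounders, and there are no baseline data. The 1.5 to 2 SD shifts are assumptions.
- **That adjustment is weakest where confounding is strongest.** The Quade difference is (1 − R²) times the jointly adjusted effect, so it is zero when that effect is zero. With no adjusted effect and correlation 0.5, an unadjusted rank test rejected 32% of the time at 1 SD and 86% at 2 SD; Quade's test rejected about 3% and 0.7%. It guards against confounding and over-corrects in significance.
- **That Quade's test always finds less than the plan's unadjusted test.** The attenuation is relative to the jointly adjusted effect. Against Mann-Whitney, Quade's test can reject more or less often.

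**Conclusion.** The point holds as a low-cost improvement and does not threaten the main comparisons. Where a covariate differs between groups, following the plan gives an adjusted non-parametric difference multiplied by 1 − R² and a test with less than its nominal 5% error. The identity is exact. The size in this study is not known, because it depends on an imbalance the documents do not report. Under the assumed settings the loss is negligible up to 0.5 SD (about 3 power points or less), about 10 to 11 points at 1 SD and about 32 to 34 points at 2 SD. At the upper end, much of the gap reflects unequal type I error (0.7% vs about 6%). That conservatism is still a real cost at the planned 0.05 threshold, and the reported difference would be understated whatever the p value. At 2 SD with 20 per group, the groups overlap little and any adjustment leans heavily on its model.

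**What to change.** For outcomes still non-normal after transformation, make the adjusted group comparison in one model containing group and the covariates. Suitable choices are cumulative-logit (proportional-odds) regression on the continuous outcome, or rank ANCOVA with group in the model. State this under Continuous variables without repeated measures, and name the same method for AUCs under Continuous variables with repeated measures. Name the covariates in advance, since either method needs them. Keep Quade's test as a sensitivity analysis, and leave the Mann-Whitney comparison as it is.

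The cost is SAP wording. The methods are available in R, which the plan already specifies, and no extra data or participants are needed. The downside is slight liberality at extreme imbalance: type I error of about 6 to 7% at 2 SD with correlation 0.5.

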### *Continuous variables with repeated measures*

Normality of measures, for each time, will be assessed using the Shapiro-Wilk test.

Differences of variables between baseline and over time within and between the groups, for normally distributed variables, will be tested by ANOVA with repeated measures on one factor (time) and Bonferroni adjustment for multiple comparisons. For non-normally distributed variables, Friedman test and pairwise Wilcoxon as a *post hoc* test will be applied.

Analysis of quartiles will be performed for both baseline values and pairwise time points ( $\Delta$ ) upon milk ingestion.

For these variables with repeated measures, the total area under the curves (AUCs) will be also estimated using the linear trapezoidal rule, and differences in AUCs between the groups will be assessed by proper parametric or non-parametric analyses including as covariates the potential confounding variables measured at baseline.

Pearson's correlation coefficients will be calculated to assess bivariate associations among continuous variables at baseline or partial associations of estimated AUCs controlling for baseline values for variables with repeated measures.

Spearman's rank correlation will be used to assess association between non-parametric variables collected and microbiota related variables (e. g. species abundance and genes abundance).

In order to explore differences in microbiome profiles, a Partial Least Squares Discriminant Analysis was applied.

Furthermore, principal component analyses (PCA) on specific variables at baseline or unstandardised residuals correlation between AUCs and related baseline values will be also performed in order to extract features relevant to the cluster structure. Moreover, statistical significance of the distance between groups in the PCA analysis will be computed using the Hotelling T2 test.

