### *Milk test*

During the week before the milk test, subjects will fill a food diary. Moreover they will be instructed to not drink any milk, dairy product and any food product containing milk proteins during the 2 days before the milk test. On the day of the milk test, fasting subjects will fill out questionnaires about their actual appetite and GI symptoms, baseline urine and blood samples will be collected, and fasting glycaemia by finger-prick will be measured (time 0). Subsequently, subjects will drink 250 ml of milk within 10 min and thereafter, glycaemia, symptoms and appetite questionnaires, as well as blood samples and urine will be collected at specific time points (time 0.5, 1, 2, 4 and 6 hours after milk ingestion). After the last blood drawing, subjects will be offered lunch and, before leaving the study centre, they will be instructed to fill out GI symptoms and appetite questionnaires, to collect urine, to

fill out a 1-day food diary, and to consume a fixed dinner. Questionnaires, diaries and 6-24h urine samples will be delivered to the laboratory on the next day.

Blood samples will be centrifuged at 4°C and 4000 rpm; serum, plasma and plasma + aprotinin samples will be aliquoted and stored at -40°C.

Plasma samples will be analyzed for:

- casein digestion-derived peptides (beta-casomorphins and all known peptides derived from milk proteins);
- aminoacid profile;
- endocannabinoids and N-acyl-ethanolamines (ECs).

Plasma samples added with aprotinin will be analyzed for:

- gastro-intestinal hormones (in plasma samples pre-treated with aprotinin): insulin, GIP, GLP-1, glucagon, c-peptide, ghrelin, leptin.

Serum samples will be analyzed for:

- DPPIV activity;
- baseline DPPIV concentration.

In urine samples, aliquoted (1.5 ml) and frozen at -40°C, all the following analytes will be measured:

- lactose excretion levels;
- galactose + glucose excretion levels;
- indican excretion levels;
- baseline creatinine concentration.

Subjects will be also asked to collect a fecal sample under usual dietary habits and to fill out questionnaires as follows:

- physical activity questionnaire (short version of the IPAQ);
- questionnaire on quality of life;
- questionnaire on depression, anxiety and stress (DASS);
- semi-quantitative food frequency questionnaire (FFQ);
- the King's Stool Chart, to evaluate frequency and consistency of feces;
- Three Factor Eating Questionnaire (TFEQ) to evaluate individual eating behaviour.

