## Statistical analysis plan

### Sample size calculation

The sample size for this study has been calculated on the basis of the primary endpoints here listed:

- milk-derived peptides plasma concentrations after milk consumption;
- lactose urinary excretion after milk consumption;
- post-prandial plasma profile of GI hormones and ECs.

Considering circulating mean values and standard deviations reported by Deth et al. (2016) in blood of healthy population, power analysis indicated that a sample size of 19 participants per group is sufficient to detect a minimum variation of 40% in circulating BCM-7 with a power of 80% and an  $\alpha = 0.05$ .

Considering excreted % of lactose in urine, hydrogen concentration in breath and relative standard deviations as reported by Bezerra et al. (1990) a sample size of 19 participants per group is sufficient to detect a 15% minimum variation of lactose and a 50% minimum variation of hydrogen in healthy subjects, with a power of 80% and an  $\alpha = 0.05$ .

Regarding post-prandial plasma profile of GI hormones and ECs, our previous studies showed that a sample size of 13 participants is adequate to find significant differences with an 80% power and an  $\alpha = 0.05$ . (Mennella et al., 2015; Mennella et al., 2016).

The participant number will be increased up to 40 (20 subjects per group) in view of possible dropouts.

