### Statistical analysis

Data will be expressed as means  $\pm$  SEMs, unless otherwise specified.

Two-tailed P values lower than 0.05 were considered significantly different

Missing data will be handled as such, i.e., no imputation of missing data will be performed.

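### Normality is tested at each of six times, but one ANOVA-or-Friedman choice is made per variable with no rule for combining the results, so chance can decide whether groups are compared over time

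*Combined protocol and SAP*

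**What the plan says.** The SAP section on continuous variables with repeated measures sets the check: "Normality of measures, for each time, will be assessed using the Shapiro-Wilk test". Two routes follow, each chosen for the variable as a whole. One is "for normally distributed variables, will be tested by ANOVA with repeated measures on one factor (time) and Bonferroni adjustment for multiple comparisons". The other begins "For non-normally distributed variables, Friedman test and pairwise Wilcoxon", with Wilcoxon as the post hoc test. The same section promises differences over time both within and between the groups, and it separately compares total AUCs between groups with baseline covariates.

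The parent section on continuous variables puts a step before the non-parametric route: "For non-normal variables showing a significant positive skewness, logarithmic, square-root, exponential, or inverse transformation will be applied". Only variables that are still non-normal afterwards go to non-parametric tests.

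Neither section says how the time-specific results are combined, whether each test uses all subjects or one group, or what happens when the times disagree.

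**The concern.** Several tests feed one decision. If a variable must pass at every time to count as normal, the chance of failing at least once is well above the 5% of a single test, even when the data are perfectly normal.

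The two routes do not answer the same question. A repeated-measures ANOVA with group as a between-subject factor can test whether the groups differ in their time course. Friedman compares times within subjects and has no group factor, and Wilcoxon as its post hoc test most naturally compares pairs of times. A chance rejection at one time could therefore remove the between-group time-course comparison for a plasma peptide, hormone or endocannabinoid. Those profiles are primary objectives, and the study exists to compare the two groups on them. If the combining rule is settled only after the data are seen, the method for a primary endpoint is also chosen after the data are seen.

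**Working it through.** The plan states no misrouting rate, so there is no figure to reproduce.

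**Inputs from the documents**
- Times: one at baseline ("fasting glycaemia by finger-prick will be measured (time 0", when blood is also drawn) and five after milk ("blood samples and urine will be collected at specific time points (time 0.5, 1, 2, 4 and 6 hours after milk ingestion"), so six for blood analytes.
- Sample size: "The participant number will be increased up to 40 (20 subjects per group) in view of possible dropouts".
- Test level: "Two-tailed P values lower than 0.05 were considered significantly different". No separate level is given for Shapiro-Wilk, so 0.05 is assumed.

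**Assumptions**
- Any one rejection disqualifies the variable.
- Testing is either pooled (n = 40, 6 tests) or by group (n = 20 each, 12 tests).
- Within-subject correlation is not given, so 0 to 0.95 was examined.

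**Step 1: truly normal analyte, independent times**
- Pooled: 1 − 0.95^6 = 26.5%.
- By group: 1 − 0.95^12 = 46.0%.

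**Step 2: truly normal analyte, correlated times.** Simulation with 2,000 runs per setting. Each cell gives compound symmetry / AR(1). The Monte Carlo standard error is about 1 percentage point: √(0.265 × 0.735 / 2000) = 0.010.

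| Correlation | Pooled, any rejection | By group, any rejection | Pooled, after a transformation attempt |
|---|---|---|---|
| 0 | 28.1 / 26.4% | 45.5 / 44.4% | 25.6 / 23.9% |
| 0.3 | 27.3 / 25.9% | 44.6 / 45.9% | 25.0 / 23.7% |
| 0.5 | 28.8 / 27.9% | 46.4 / 45.2% | 25.6 / 25.1% |
| 0.7 | 24.2 / 26.6% | 44.5 / 46.4% | 19.5 / 23.4% |
| 0.8 | 22.6 / 24.1% | 40.2 / 43.2% | 18.0 / 20.3% |
| 0.9 | 17.2 / 21.1% | 32.4 / 39.3% | 13.4 / 16.7% |
| 0.95 | 15.5 / 16.2% | 29.3 / 31.7% | 11.8 / 12.0% |

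The last column assumes a coefficient of variation of 30% and applies a transformation to the whole variable, which is then retested at all six times. The ranges are 16-29% pooled, 29-46% by group, and 12-26% pooled after a transformation attempt.

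**Step 3: a different combining rule.** Suppose at least 4 of 6 rejections are needed and times are independent:

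15 × 0.05^4 × 0.95^2 + 6 × 0.05^5 × 0.95 + 0.05^6 = 0.000086, below 0.01%.

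Correlation raises this, but it cannot exceed the expected number of rejections divided by four: 6 × 0.05 / 4 = 7.5%.

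**Step 4: scale of the effect.** The milk test section names seven hormones. If all seven were truly normal and any rejection counted, the expected number failing on the raw scale would run from 7 × 0.16 = 1.1 to 7 × 0.46 = 3.2.

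**The case against.** The strongest reply is that the any-rejection rule is not in the SAP. That is correct. The documents are compatible with rates from near zero to about 46%, depending on a rule they do not state. What survives is that the rule is missing, that the most natural reading gives a rate several times 5%, and that the choice governs primary analytes.

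A reader might go further in four ways that the documents do not support.

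- **Mixed scales within one profile.** One might infer that failing times are transformed and the others left raw. The transformation clause speaks of variables, and the natural reading is one transformation per variable. The SAP does not expressly require a common scale, but it does not prescribe a mixture either.
- **Most skewed analytes get conflicting results across times.** On the raw scale this is often so for mild to moderate skewness. With pooled testing, lognormal data of skewness 1.3 and correlation 0.3 to 0.5 gave mixed results in 84-89% of runs. With skewness of 3.7 or more, pooled testing rejects at nearly every time and 5% or fewer are mixed. These are also results before the SAP's transformation step. A lognormal analyte is normal after a log transformation and then faces the same chance-rejection problem as any normal analyte.
- **The wrong quantity is tested.** The ANOVA assumption concerns residuals, but Shapiro-Wilk is unaffected by a shift in mean. Testing each group at each time therefore amounts to testing residuals within group-by-time cells. The objection applies only to pooled testing, where a real group difference enters the distribution being tested.
- **The group comparison is lost altogether.** It is not. The AUC comparison between groups stands on either route.

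It is also fair to say that no inflation of type I error or loss of power has been shown here, and that most truly normal analytes would still reach the ANOVA under every scenario examined.

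**Conclusion.** The point holds in a conditional form. The SAP applies six time-specific normality tests, makes one choice of method per variable, and gives neither a combining rule nor the unit of testing. If any rejection disqualifies, a truly normal analyte leaves the ANOVA in about 16-29% of cases (pooled) or 29-46% (by group). A transformation attempt reduces the pooled rate to about 12-26%, and a majority rule makes it near zero with independent times. These figures rest on the 0.05 level, 20 subjects per group and an unstated within-subject correlation taken from 0 to 0.95.

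The consequence is specific: a diverted analyte has no between-group test of its time course, while its AUC comparison remains. That makes this worth correcting before analysis. It does not show that the primary comparisons are invalid.

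**What to change.** Replace the per-time Shapiro-Wilk tests with one decision per analyte. The SAP should state that:

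- each analyte is analysed on a single scale at all six times and in both groups, for example log for positively skewed concentrations;
- the scale is checked once, on the residuals of the fitted group-by-time repeated-measures model;
- no Shapiro-Wilk P value from a single time point selects the method.

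If a rank-based fallback is kept, the SAP should say what triggers it and how the groups are then compared over time.

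The cost is SAP wording only, with no new data, subjects or procedures. The small downside is that a residual check needs some judgement. The documents give no analyte distributions, so the log scale is offered as an example and cannot be justified from them for any particular analyte.

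### Repeated measures that stay non-normal have no named test comparing the two groups over time; Friedman and paired Wilcoxon cannot do it, and AUC largely misses timing

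*Combined protocol and SAP*

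**What the plan says.** All of this is in the statistical analysis plan of the combined document.

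- *Continuous variables* sends a variable to rank methods only after transformation has failed: "For those variables which will not show a normal distribution after arithmetic transformation, non-parametric tests will be used".
- *Continuous variables with repeated measures* checks the distribution at every time: "Normality of measures, for each time, will be assessed using the Shapiro-Wilk test".
- The same section states a between-group aim: "Differences of variables between baseline and over time within and between the groups, for normally distributed variables" are to be tested by repeated-measures ANOVA with time as the repeated factor and a Bonferroni adjustment. That design can carry group as a between-subject factor.
- The non-normal counterpart is one sentence: "For non-normally distributed variables, Friedman test and pairwise Wilcoxon as a" post hoc test. It mentions neither group nor Bonferroni.
- The section adds three analyses. AUCs are compared between groups by "proper parametric or non-parametric analyses including as covariates the potential confounding variables measured at baseline". A quartile analysis is described as "Analysis of quartiles will be performed for both baseline values and pairwise time points". The third is "principal component analyses (PCA) on specific variables at baseline or unstandardised residuals correlation between AUCs and related baseline values", for which "statistical significance of the distance between groups in the PCA analysis will be computed using the Hotelling T2 test".
- Mann-Whitney and Quade's test are named only under *Continuous variables without repeated measures*.

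**The concern.** The trial compares two groups, and its primary endpoints include post-milk plasma peptides and the post-prandial profiles of GI hormones and endocannabinoids, sampled at 0, 0.5, 1, 2, 4 and 6 h. For a variable in the non-normal branch, the only time-course test named answers a different question: whether values change over time. A significant result would be expected simply because everyone drank milk.

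Two consequences follow. A group difference in when the response occurs could go undetected. And a significant Friedman test, or significance in one group and not in the other, could be reported as a group difference.

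**Working it through.** **1. What each planned analysis can see in this branch**

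- *Friedman, paired Wilcoxon:* time effects within subjects. In a direct check on one data set of 38 subjects by 6 times, the Friedman statistic was 6.2556. It stayed at 6.2556 when one group's values were tripled and when subjects were permuted across groups. This needs no distributional assumption.
- *AUC:* a group comparison, but on one number per subject.
- *PCA with Hotelling:* a group comparison, but on baseline variables or AUC residuals, so without information on time points.
- *Quartiles of changes:* no group contrast named.

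**2. How AUC weights the samples**

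The trapezoidal rule at the planned times gives weights 0.25, 0.5, 0.75, 1.5, 2 and 1, which sum to 6. The 0.5 h sample carries 0.5/6 = 8%, the 1 h sample 0.75/6 = 13%, and the last three together 4.5/6 = 75%.

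**3. Hand check, normal data**

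Assumptions: unit SD, within-subject correlation 0.5, n = 20 per group. Unit curves are (0, 1, 0.6, 0.3, 0.1, 0) for the 0.5 h peak and (0, 0.2, 0.6, 1, 0.3, 0) for the 2 h peak, both with height 1.5 SD. Power ≈ Φ(δ√(n/2) − z).

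- AUC: unit areas are 1.60 and 2.65, so the difference is 1.5 × 1.05 = 1.575. The variance is 0.5 × 6² + 0.5 × 8.125 = 22.06 (8.125 is the sum of squared weights), so SD = 4.70. Then δ = 1.575/4.70 = 0.335 and power ≈ Φ(0.335 × 3.16 − 1.96) = Φ(−0.90) ≈ 18%.
- Change at 0.5 h alone: SD = √(2 × (1 − 0.5)) = 1 and δ = 1.5 × (1 − 0.2) = 1.2. At level 0.05/5 = 0.01, power ≈ Φ(1.2 × 3.16 − 2.58) = Φ(1.21) ≈ 89%, before counting the other four times.

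**4. Simulation**

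2,000 runs, same settings; the standard error is at most √(0.25/2000) = 1.1 percentage points. Entries are % significant for normal / heavy-tailed t(3 df) / detection-limit data with about half of fasting values tied. Quade's test uses the baseline value as covariate. The change test is Mann-Whitney at five post-milk times with Bonferroni.

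| Scenario | AUC, Mann-Whitney | AUC, Quade | Change test | Rank group-by-time |
|---|---|---|---|---|
| Peak 0.5 h vs 2 h, 1.5 SD | 16/25/19 | 24/38/26 | 98/100/99 | 100/100/100 |
| Same, 1 SD | 10/14/10 | 14/19/13 | 62/86/64 | 95/100/93 |
| Rise at 0.5 h in one group only, 1.5 SD | 7/9/14 | 9/12/18 | 97/100/97 | 99/100/98 |
| One response half the other, peak 1.5 SD | 32/47/40 | 49/66/53 | 46/67/53 | – |
| Flat curves, constant shift 0.93 SD | 94/99/95 | 48/58/50 | – | – |

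Friedman rejected in 5/5/5% for the constant shift. When both groups responded identically it rejected in 100/100/100%, while the between-group tests stayed at 3–5%. The shift of 0.93 SD is what a two-sample t test with the plan's 19 per group detects with 80% power at two-sided 0.05.

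A separate simulation (log-normal data with log-SD 0.5, 19 per group, 3,000 runs) used curves of different shape with equal area at the median. Mann-Whitney on AUC rejected in 3.8%, and Bonferroni-adjusted Mann-Whitney at the five post-milk times in 87.5%.

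**5. How a variable gets here**

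The plan does not say how many failed normality tests among the six times are enough. If one is enough, truly normal data fail in 27% of runs (40 subjects pooled) or 46% (tested by group), before any transformation. Milk peptides are a plausible case: subjects avoid milk proteins for 2 days, so fasting values may sit at the detection limit (an inference), and no transformation removes ties. With a quarter or half of fasting values tied, 98–100% fail.

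**6. Side point: Bonferroni**

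If the Wilcoxon tests were left unadjusted, with a true change of 2 SD at 1 h only, at least one false positive appears in 16/15% of runs (normal / t(3 df)) over the four other baseline contrasts and in 30/31% over the ten other pairs. With Bonferroni it is 3%.

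**The case against.** Every variable in this branch does get a between-group test, through AUC. The plan states no hypothesis about timing; it is sized on a 40% difference in BCM-7, which is a matter of level, and AUC handles level well. The near-100% figures come from large effects with shapes that AUC handles badly. With the same two curves at 0.5 SD, AUC gives 6–8%, the change test 14–28% and the group-by-time test 30–66%. Reaching the branch is uncertain: transformation comes first, the one-failure rule is assumed, and no detection limit or fasting level is given. An analyst could also borrow Mann-Whitney for single times or changes.

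Much of this stands as a limit on size. AUC protects overall level and, when adjusted for baseline, amplitude; the curve shapes are assumptions; the number of affected variables is unknown. It does not remove the defect. The section states a between-group aim over time and adds AUC as a further analysis, and the primary endpoints are described as profiles. Borrowing Mann-Whitney is not in the plan and would be a choice made after seeing the data.

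**Conclusion.** The concern holds. For repeated measures that stay non-normal, the named time-course tests cannot answer the between-group question that the section poses, and no other planned analysis compares the groups by time point. That part follows from the text and from how Friedman works.

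The size is conditional on the assumed shapes, correlation and 20 per group. For a shift in peak time of 1 to 1.5 SD, AUC tests have 10–38% power, against 62–100% for the change test and 93–100% for the rank group-by-time test. There is no material loss for amplitude if AUC is adjusted for baseline, nor for overall level with Mann-Whitney on AUC. The plan should be corrected before analysis, but the group comparison is not lost altogether.

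**What to change.** For repeated measures that remain non-normal:

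1. Name in advance one between-group time-course analysis. Either test group and group-by-time with a rank-based factorial repeated-measures method (ANOVA-type statistic), or apply Mann-Whitney to change from baseline at each of the five post-milk times, with Bonferroni (0.01 each) or Holm. Prefer the factorial test for markers with many values at the detection limit: there, a pure level shift on top of a common response makes the change test reject in 13% of runs, against 6% for the group-by-time test.
2. Keep the AUC comparison, with Mann-Whitney for overall level. If Quade's test with the baseline value is also used, state that it tests response given baseline and is not interchangeable with Mann-Whitney (48–58% versus 94–99% power for the constant 0.93 SD shift).
3. Label Friedman and paired Wilcoxon as within-group analyses, state that Bonferroni also covers the Wilcoxon tests, and rule out inferring a group difference from significance in one group only.

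The cost is SAP wording; no new data, visits or samples are needed, and R is already planned. The change option adds 5 tests per analyte, so 7 × 5 = 35 if all seven listed hormones came this way, with adjustment only within each analyte. The factorial test is global and does not show at which time the groups differ.
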